## 1.2 Rationale

In Colombia, the death rate from CVD in 2014 was 146.9 per 100.000 population. In this country, 30% of all deaths and 16.3% of Years of Life Lost can be attributed to CVD (14). The Colombian health system is divided in two different regimes, according to individuals' payment capacity. People able to contribute to the social security system and their beneficiaries are affiliated to the Contributory Regime, which is compulsory for formal employees and pensioners. The Subsidized Regime is financed by the State and covers the poor un-employed or informal-employed population. In Colombia, in the context of a market-oriented health system, cost-containment mechanisms imposed by health insurance companies often hamper timely access to health care, especially for those chronically ill, generating harmful consequences to people's lives (15).

In 2016 we carried out a cross-sectional survey in a low-income urban community in Medellin, aimed to estimate the prevalence of hypertension among the population aged 35 years or older and the magnitude and the determinants of the main gaps in hypertension care and control (Table 1).

**Table 1.** Main Gaps in hypertension care and control – definitions.

Gap	Numerator	Denominator	Remarks
Diagnosis	Number of unaware hypertensive individuals	The total surveyed population	Also calculated for hypertensives (nr. unaware /total hypertensives)
Pharmacological treatment	Number of aware hypertensive individuals who received prescription of antihypertensive medications but do not take any antihypertensive drug	Aware hypertensive individuals who received prescription of antihypertensive medications	
Follow-up	Number of aware hypertensive individuals who did not receive a follow-up consultation in the last year	Number of aware hypertensive individuals	

Control	Number of aware hypertensives with uncontrolled hypertension + Number of unaware hypertensives	The total hypertensive population (aware + unaware)	Also calculated in subgroup aware hypertensives
---------	--	---	---

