The study showed a prevalence of hypertension of 43.4%. Among the total hypertensive individuals, 36.7% were unaware of their diagnosis. Of the aware hypertensives, 93% had been prescribed pharmacological treatment, but 7% of those who had been prescribed treatment were not taking any medication and only 65% of those taking treatment referred treatment compliance. Moreover, 15% of the aware hypertensives did not have any follow-up consultation during the previous year. Among the aware hypertensives, 41% had uncontrolled hypertension. Nineteen percent of aware hypertensives and 45% of unaware hypertensives did not have contact with formal health services in the last year, mainly because they did not feel the need. On the other hand, 55% of unaware hypertensives accessed to health care in the previous year but health services failed to diagnose them.

Studies specifically aimed at reducing the gaps and barriers to hypertension care and control at population level in the country are needed.

The results of the baseline study, the possible determinants of the identified gaps and potential solutions were discussed in a workshop held in Medellin-city, with the participation of ITM staff, the University of Antioquia and Metrosalud. A summary of the identified potential determinants of the main gaps, mainly related to disease detection and quality of care, is presented in Table 2.

**Table 2. Potential determinants at health provider, population and health system level of the main health coverage gaps for hypertension care and control in the Santa Cruz Commune**

Hypertension Coverage Gap / Source of barriers	Health Provision	Population	Health Services
Diagnosis Gap	
 
- No measurement of blood pressure during health care contacts
 
- High blood pressure is detected but confirmation of diagnosis fails due to lack of continuity of care
 
	
 
- Low risk perception of hypertension
 
- Mild or no symptoms determine health seeking
 
	
 
- Passive and fragmented health services
 
- Limited opening hours of services for hypertension detection
 

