#### 4.1.4 Definitions

Hypertensive individual (operational definition for survey): self-report of previously diagnosed hypertension or without previous diagnosis but presenting an average blood pressure (BP) measurement higher than 140/90 mmHg(11;16).

Presumptive hypertensive individual: no self-report of previously diagnosed hypertension but presenting an average BP measurement higher than 140/90 mmHg.

Controlled hypertensive individual: self-report of previously diagnosed hypertension and an average BP less than 140/90 mm Hg for patients between 35 and 59 years old or diabetics and 150/90 mm Hg for patients aged 60 years or older (17).

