## **4.2 Procedures**

A multi-component intervention, detailed below, will be implemented in the intervention area, while standard hypertension care will be provided in the control area.

Each intervention component will be standardized and described in a field manual for the improvement of hypertension management. For each component we will clearly define: subcomponents or activities specifying implementation level and units, responsible, target population, content, methodology and way of delivery, time, duration, key improvement factors, functioning principles and expected results per activity.

A logic model of the intervention will be elaborated to provide a graphical depiction of the inputs, processes, immediate, short-term, and long-term outcomes, and the relationship and sequence between the different intervention components and critical points in the implementation process as a whole. Critical points are stages or activities in the process, susceptible to be measured, in the

absence of which other stages or activities cannot be implemented. The intervention activities will be implemented by Metrosalud staff of the health structures in the Commune with technical assistance from the investigation team.

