##### **A. Health services organization**

A.1. Hypertension screening: 1) all adults aged 35 years or older presenting to any health service (including clinical and support services) will be asked if they had their BP measured in the previous year. If not, they will be referred to a specific nursing hypertension service (“Healthy Hearts” service, see A.2 below) for a BP measurement, using a ticket stub for referral. 2) Doctors and nurses encountering presumptive hypertensive patients (individuals not reporting a previous diagnosis of hypertension but presenting BP higher than 140/90), will refer them to the “Healthy Hearts” service for confirmation of the diagnosis with serial BP measurement. 3) The entire health care flow for patients with a high BP measurement within health facilities will be standardized in order to guarantee continuity of care and correct diagnosis.

A.2. “Healthy Hearts” service: an auxiliary nursing station with extended opening hours and providing services such as BP measurement, global cardiovascular risk assessment and preventive counselling. It oversees serial self-measured BP monitoring within the health facility premises to exclude white coat hypertension, providing devices and patient education on self BP measurement. It will ensure retention and follow-up of all people with a high BP measurement at screening (at service level or in the community - see C.2 below) in order to guarantee that final diagnosis (hypertensive or not) is reached. It will refer to clinicians of the CVRP all newly diagnosed hypertensive patients. Through phone calls and/or SMS to patients and linkage with community agents, it will promote effective referral and manage non-attendance to follow-up CVRP consultations. It will administer periodical anonymous exit-questionnaires (annex 6) to hypertensive patients exiting from CVRP

consultations in order to assess effective BP measurement and the quality of pharmacological and non-pharmacological advice during medical consultations. Results will be transmitted to the cardiovascular risk team (see A.3.1 below).

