## C. Patients and community engagement

- C.1. Patient empowerment: sessions where "expert hypertensive patients" will provide support and peer-education to other patients in need, such as those newly diagnosed or non-adherent to treatment or with uncontrolled hypertension, under the supervision of a social worker.
- C.2. Community engagement: A Community Hypertension Outreach Group (CHOG) will be set up, composed by three voluntary community health workers who will be trained and certified. The CHOG will be created in partnership with the patients' association, which is a very dynamic organization already present in the Commune and interested in engaging in the project. The CHOG will conduct screening activities with measurements of BP in selected public areas of the commune on a weekly rotation basis, for all adults without BP readings in the previous year and referral of those with a positive screening to the nearest health facility for diagnosis confirmation. The CHOG will provide health education with emphasis on healthy lifestyles (tobacco cessation, physical activity and healthy diet). It will contribute to increase community awareness on the importance of hypertension control and on cardiovascular risk detection and prevention. Existing local communication channels such as the community radio and the local newspaper will also be used.

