17. Result of serial BP measurement	Number of patients with average systolic BP $\geq 140$ mm Hg or diastolic BP $\geq 90$ mm Hg at	Number of individuals receiving serial BP measurements	Register of serial BP measurements at Healthy Hearts service	Referral service (Healthy Hearts service, clinical services or CHOG)	Monthly

	serial BP measurement			Age, sex, patient or caretaker, chronic patient (yes, no) Cardiovascular risk level.	
18. Indication of serial self-measured BP monitoring	Number of individuals with indication of serial self-measured BP monitoring	Number of individuals with average systolic BP $\geq 140$ mm Hg or diastolic BP $\geq 90$ mm Hg as result of a serial BP measurement	Register of serial self-measured BP monitoring at Healthy Hearts service	Age, sex, patient or caretaker, health insurance scheme	Monthly
19. Realization of serial self-measured BP monitoring	Number of patients with serial self-measured BP monitoring	Number of patients with indication of serial self-measured BP monitoring	Register of serial self-measured BP monitoring at Healthy Hearts services	Age, sex, patient or caretaker, health insurance scheme	Monthly
20. Result of serial self-measured BP monitoring	Number of patients with average systolic BP $\geq 140$ mm Hg or diastolic BP $\geq 90$ mm Hg as result of a serial self-measured BP monitoring	Number of patients with serial self-measured BP monitoring	Register of serial self-measured BP monitoring at Healthy Hearts services	Age, sex, patient or caretaker,	Monthly

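### If 140/90 means SBP or DBP, non-diabetics aged 60 or over with SBP above 140 and below 150 and DBP below 90 leave the control gap on diagnosis at unchanged BP, so the difference-in-differences may overstate better BP control

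*Combined protocol and SAP*

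**What the plan says.** - **Who is hypertensive (4.1.4).** Anyone who reports a diagnosis, and anyone "without previous diagnosis but presenting an average blood pressure (BP) measurement higher than 140/90 mmHg". There is no age split, and the text does not say whether one component above its limit is enough.
- **Who is controlled (4.1.4).** Only a person with a reported diagnosis can be controlled. The limit is 140/90 at ages 35 to 59 "or diabetics and 150/90 mm Hg for patients aged 60 years or older". I read this as 140/90 for diabetics of any age and 150/90 for non-diabetics from 60.
- **Control gap (1.2, Table 1).** The numerator is "Number of aware hypertensives with uncontrolled hypertension + Number of unaware hypertensives"; the denominator is all hypertensives. A version among aware hypertensives is also planned.
- **Screening (4.2.1).** A.1 refers to the Healthy Hearts service "individuals not reporting a previous diagnosis of hypertension but presenting BP higher than 140/90". In Table 4, indicators 17, 18 and 20 join the two components with an or ("mm Hg or diastolic BP"). C.2 adds community screening: "The CHOG will conduct screening activities with measurements of BP in selected public areas of the commune on a weekly rotation basis".
- **Where (4.2).** The package "will be implemented in the intervention area, while standard hypertension care will be provided in the control area".
- **Analysis (4.3.1).** The main outcomes are compared by difference-in-differences. No analysis with a common BP cut-off is planned.

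**The concern.** Two limits meet in one outcome. An undiagnosed person enters the gap at 140/90 whatever their age, while a diagnosed non-diabetic of 60 or over stays in it only from 150/90. For people between the two limits, diagnosis alone changes their status.

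Differencing removes what is common to both communes. It does not remove extra diagnoses that arise after baseline in one commune. The control gap is a main outcome and the one on which section 4.1.2 bases the sample size. If part of a reported fall is reclassification, the trial would credit the intervention with lower BP that nobody measured.

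**Working it through.** **1. The plan's own figure.** Section 4.1.2: gap 45%, difference 10 points, power 0.75, alpha 0.10. For 45% versus 35%, two-sided:

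n = [1.645 × √(2 × 0.40 × 0.60) + 0.674 × √(0.45 × 0.55 + 0.35 × 0.65)]² / 0.10² ≈ 258 per commune, or 278 with continuity correction. The stated 280 is reproduced, so 10 points is the yardstick.

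**2. The definitions applied at fixed BP, SBP-or-DBP reading.**

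| Person | Unaware | Diagnosed, same BP |
|---|---|---|
| 65, non-diabetic, 145/80 | in gap | **out of gap, still in denominator** |
| 65, non-diabetic, 145/95 | in gap | in gap |
| 65, diabetic, 145/80 | in gap | in gap |
| 50, non-diabetic, 145/80 | in gap | in gap |
| 65, non-diabetic, 155/80 | in gap | in gap |

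Only the first profile moves. There is a small opposite effect at the boundary: a person under 60 at exactly 140 is not above 140 when undiagnosed, and not below 140 once diagnosed.

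**3. Size of the shift.** Inputs from the 2016 survey (1.2), used as a stand-in because the two-commune baseline results are not in the documents: 36.7% of hypertensives unaware; 41% of the aware uncontrolled. Per 100 hypertensives, the gap is 36.7 + 0.41 × 63.3 = 36.7 + 25.95 = 62.65. (The plan assumes 45%; that is a separate matter.)

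Let f be the share of unaware hypertensives in the band, and k the extra share of them diagnosed in the intervention commune, net of control. Both are assumed.

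Shift = 36.7 × f × k points:
- f = 10%, k = 10%: 0.37
- f = 20%, k = 25%: 1.84
- f = 30%, k = 50%: 5.51

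A k of 50% is an extreme. Section 1.2 reports that "55% of unaware hypertensives accessed to health care in the previous year but health services failed to diagnose them", but that is contact with any formal care. The facility screening is in Metrosalud units, and the survey covers all permanent residents.

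**4. What the planned aware-only gap would show.** With the same k for all unaware people and unchanged BP, it becomes (25.95 + 36.7k(1 − f)) / (63.3 + 36.7k). The smallest rise is at f = 30%, k = 10%: 28.52/66.97 = 42.6%, or +1.6 points from 41%. The largest is at f = 10%, k = 50%: 42.47/81.65 = 52.0%, or +11.0 points. It rises while the total gap falls, because newly diagnosed people outside the band enter as uncontrolled.

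**5. Does a common cut-off remove the shift?** Take f = 20%, k = 25%, and use 150/90 for aware and unaware non-diabetics from 60, with the denominator held. The gap is 62.65 − 0.20 × 36.7 = 55.3% before and 55.3% after. With 140/90 for everyone, the band stays in the gap before and after. Either way the shift from the band is zero.

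**6. Sensitivity of a population-level BP measure.** Assume both surveys are the planned size, and use the plan's 10% non-response, 40% prevalence and design effect of 1.5.
- Control gap: 1150 × 0.9 × 0.40 / 1.5 = 276 effective hypertensives per commune and survey. SE = √(4 × 0.6265 × 0.3735 / 276) = 5.82 points; 10/5.82 = 1.72.
- All surveyed: 1150 × 0.9 / 1.5 = 690 effective. The level is 0.40 × 62.65% = 25.1%, an approximation because it carries over the mixed limits. SE = √(4 × 0.2506 × 0.7494 / 690) = 3.30 points. At constant prevalence, a 10-point fall in the gap is 0.40 × 10 = 4.0 points here; 4.0/3.30 = 1.21.

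**The case against.** - **Detection is an aim.** Section 2 lists it, and Table 1 deliberately counts unaware people in the gap. So a fall through diagnosis is partly intended, and it misleads only when read as lower BP. That stands and limits the claim. But Table 1 has its own diagnosis gap, and the other four profiles above get no credit for control from diagnosis alone. The documents state no reason why this one band should.
- **The reading is borrowed.** Section 4.1.4 does not say SBP or DBP; the or comes from facility indicators, and the baseline protocol may settle it. This stands. If both components must be exceeded, the person at 145/80 is not hypertensive while unaware and joins the denominator as controlled on diagnosis. The mechanism described here would then not apply.
- **Diagnosis needs confirmation.** Component A.2 requires serial and self-measured readings to exclude white-coat hypertension. People within 10 mmHg of the limit may be among the least often confirmed, so k may be low in this band. This stands.
- **Planned outcomes already show it.** Total gap = U + (1 − U) × G, where U is the unaware share and G the aware-only gap, so a fall driven by awareness is visible. The reclassified part is not separated, however, and a real BP improvement can hide the pattern in step 4.
- **A false-positive rate.** A reader might infer one by setting the shift against the standard error and alpha 0.10. The documents do not support that: 4.1.2 attaches alpha to a comparison of the communes at endline without stating the side, and 4.3.1 gives no test or decision rule for the difference-in-differences.

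**Conclusion.** The asymmetry is real on the SBP-or-DBP reading, and only for non-diabetics aged 60 or over with survey SBP above 140 and below 150 and DBP below 90. If screening raises diagnosis in the intervention commune, the difference-in-differences on the control gap is expected to favour the intervention when it is read as better BP control.

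The size cannot be derived from the documents. The range of 0.4 to 5.5 points against 10 is an illustration from assumed f and k with 2016 inputs, and its upper end needs extreme values of both.

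A reader might infer that everyone of 60 or over with SBP in the 140s is affected, or that a fall in the gap would be mostly artefact. Neither follows: diabetics and people with DBP of 90 or more do not move, and nothing in the documents fixes f or k.

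**What to change.** Keep the Table 1 control gap as the main outcome.

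1. **Add to 4.3.1 a prespecified sensitivity analysis.** Repeat the difference-in-differences on the control gap with one BP cut-off per age and diabetes stratum, applied alike to aware and unaware people, with the hypertensive denominator as now defined. Show it for each cut-off already in 4.1.4.
2. **Report as supporting information** the difference-in-differences in the proportion of all surveyed people aged 35 or over whose measured BP is at or above each of those cut-offs, regardless of awareness. This is needed because analysis 1 still falls at unchanged BP when people at or below 140/90 at survey are newly diagnosed and enter the denominator as controlled. The population measure is not affected by that.
3. **Report both beside the main result** and interpret a fall in the gap in their light, with no pass/fail gate. At a ratio of 1.21, the population measure alone would have the wrong sign about 11% of the time under the full planned effect (Φ(−1.21)).
4. **In 4.1.4,** reconcile the two thresholds for the gap calculation, and state whether 140/90 means SBP or DBP and how values of exactly 140 or 90 are classed.

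The cost is a little extra analysis and recoding the baseline survey in the same way, with no new data. The population measure is less sensitive (1.2 versus 1.7). The 150/90 version of analysis 1 leaves some unaware hypertensives out of the numerator, unlike Table 1, so it serves only as a sensitivity analysis. No view is taken on which cut-off is clinically right.

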## **4.2 Procedures**

A multi-component intervention, detailed below, will be implemented in the intervention area, while standard hypertension care will be provided in the control area.

Each intervention component will be standardized and described in a field manual for the improvement of hypertension management. For each component we will clearly define: subcomponents or activities specifying implementation level and units, responsible, target population, content, methodology and way of delivery, time, duration, key improvement factors, functioning principles and expected results per activity.

A logic model of the intervention will be elaborated to provide a graphical depiction of the inputs, processes, immediate, short-term, and long-term outcomes, and the relationship and sequence between the different intervention components and critical points in the implementation process as a whole. Critical points are stages or activities in the process, susceptible to be measured, in the

absence of which other stages or activities cannot be implemented. The intervention activities will be implemented by Metrosalud staff of the health structures in the Commune with technical assistance from the investigation team.

#### 4.2.1 Intervention

The components of the intervention aim to integrate activities related to: A) Health services organization, B) Training of clinical staff, and C) Patients and community engagement. Taken together, through these components, most elements of the SHTP project and the Technical Package for Cardiovascular Disease Management in Primary Health Care(13) will be covered in a context-adapted intervention.

##### **A. Health services organization**

A.1. Hypertension screening: 1) all adults aged 35 years or older presenting to any health service (including clinical and support services) will be asked if they had their BP measured in the previous year. If not, they will be referred to a specific nursing hypertension service (“Healthy Hearts” service, see A.2 below) for a BP measurement, using a ticket stub for referral. 2) Doctors and nurses encountering presumptive hypertensive patients (individuals not reporting a previous diagnosis of hypertension but presenting BP higher than 140/90), will refer them to the “Healthy Hearts” service for confirmation of the diagnosis with serial BP measurement. 3) The entire health care flow for patients with a high BP measurement within health facilities will be standardized in order to guarantee continuity of care and correct diagnosis.

A.2. “Healthy Hearts” service: an auxiliary nursing station with extended opening hours and providing services such as BP measurement, global cardiovascular risk assessment and preventive counselling. It oversees serial self-measured BP monitoring within the health facility premises to exclude white coat hypertension, providing devices and patient education on self BP measurement. It will ensure retention and follow-up of all people with a high BP measurement at screening (at service level or in the community - see C.2 below) in order to guarantee that final diagnosis (hypertensive or not) is reached. It will refer to clinicians of the CVRP all newly diagnosed hypertensive patients. Through phone calls and/or SMS to patients and linkage with community agents, it will promote effective referral and manage non-attendance to follow-up CVRP consultations. It will administer periodical anonymous exit-questionnaires (annex 6) to hypertensive patients exiting from CVRP

consultations in order to assess effective BP measurement and the quality of pharmacological and non-pharmacological advice during medical consultations. Results will be transmitted to the cardiovascular risk team (see A.3.1 below).

